Severe Perinatal Depression (PND) is a major depressive episode that occurs during pregnancy or onset within 12 months of the birth of a child. The prevalence of severe PND in the general population is estimated to be 5-10% (2). PND is a seriously disabling condition and can increase the risk of self-harm and health complications in mother can deleteriously affect the cognitive, emotional and social development of the child and increases the substantial economic burden on families and society (3). Selective Serotonin Reuptake Inhibitors (SSRIs) and psychotherapy are the main available treatment modalities for PND. While they are effective in some, it takes longer to work and half of the patients do not fully recover from depression. A faster onset of antidepressant action will be critical in enabling faster relief from depression and may increase the chance of full recovery. The main objective of this study is to investigate the rapid antidepressant effect of low sub-anesthetic dose of ketamine in PND.

Aims

To assess the safety, pharmacokinetics and antidepressant efficacy of a sub-anesthetic dose of intravenous ketamine in perinatal depression

A single, intravenous, sub-anesthetic dose of ketamine in patients with Treatment-Resistant Depression (TRD) induces a significant (50%) reduction in depression symptoms within 2 hours of administration with 65% of depressed patients respond by 24 hours and up to 35% maintain response until the end of 1 week (4). Our in-house pilot data, in consistent with worldwide studies, show that ketamine (N=5) can be safely administered to depressed patients and improves depression symptoms when assessed at 24 hrs post infusion. Ketamine has not been studied in the treatment of PND where there is a significant unmet need.

The dosing of ketamine (0.5 mg/kg over 40 mins) for antidepressant treatment was developed from research studies in the 1990s based on use in healthy participants (36). However, newer studies show some patients respond to lower dose and tolerated better (fewer side effects) by the patients (37). IV Ketamine reaches a peak within a few mins with an elimination half-life of 2–3 hrs (38). Ketamine's clearance may be 20% higher in women than in men (39). Ketamine is mostly metabolized in norketamine (80%) and persists more than 5 h after administration (38). It is important to evaluate ketamine's pharmacokinetic data in PND to improve safety for the

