Research Design and Methods: All human subjects' research will be conducted with full approval from the IRB at the University of Texas Health Science at Houston. We will recruit PND patients (N=10) who will be administered a single intravenous infusion of Ketamine either at 0.5 mg/kg or 0.2 mg/kg over 40 minutes in a double-blinded and crossover fashion separated by minimum 7 days, with the order being randomized and balanced across subjects. Two doses will help decide the safe, tolerable and effective dose for PND subjects will undergo a standard screening interview visit to confirm eligibility evaluations including SCID-4 interview (27) and collection of demographic, clinical and medical history. To ensure medical stability, each patient will have a physical examination and urine toxicology screen to rule out the recent undisclosed use of illicit substances. It will also be requested that the patient provide a record of lab results to indicate adequate health for inclusion.

We will pre-screen potential participants over the phone to minimize the invitation to non-eligible participants. Eligible patients that want to participate in the study will be scheduled to have a screening visit to review consent and determine eligibility.

The total duration of the commitment of the study is minimum of 4 weeks. Extension of the timeline can occur depending on the time between the screening visit and the first infusion dose. The total commitment should not exceed 3 months. There will be a minimum 7 days between the 2 infusions. Patients who qualify will complete the infusions on another day at UTHealth Clinical Research Unit at Memorial Hermann-TMC, Houston. University of Texas Health Science Center at Houston Memorial Hermann-TMC [name] or at our Harris County Psychiatric Center (HCPC) where they will be given the ketamine infusion by the study nurse. Patients will be advised to follow the American Association Preoperative Fasting Guidelines prior to infusion.

There will be two appointments where they will be administered a single intravenous infusion of Ketamine either at 0.5 mg/kg or 0.2 mg/kg over 40 minutes in the first infusion visit and a second infusion visit where they will receive the infusion that was not given on the first visit, where there will be a minimum of 7 days between infusions.

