Placement of IV: For both of the infusion days, after the initial evaluation is done, patients will be placed one intravenous line in each arm. One line will be used for the ketamine infusion and the other line will be used for the collection of blood samples and to reduce discomfort for patients with frequent blood draws. If the sample is not obtained from the IV line due to clotting, the patient will be asked if they would like to have a blood draw using a BD Vacutainer.

Medical Monitoring: During the infusion, patients will receive continuous monitoring from the nurse and the attending and after the completion of 40 min infusion, patients will rest for two hours under the observation of clinical nurse and reassessed again by anesthesiologist/psychiatrist (advance life support trained) at 2 hours after infusion. Patients will be discharged from the hospital unit between 2-4 hours after the infusion with a responsible adult for the study visit. Patients will be contacted on days 1, 2 and 7 post-infusion for a follow-up assessment of mental state by telephone and will be scheduled for study visits.

Stopping Rules: Any worsening of depression symptoms - if patients score a 3 on item 3 of the HDRS or 3 on item 10 of the MADRS or total HDRS score (first 21-items) increases by 5 points or more from one visit to the next weekly visit. The C-SSRS will be administered to monitor suicidal ideation and behavior. Increased observation consists of daily phone calls with study physicians and/or increasing visit frequency based on the PI's clinical judgment.

Blood tests: Ketamine and norketamine plasma levels will be collected before and 30 minutes, 2 hours and 4 to 5 hours after the infusion. Samples will be stored at BBSB for analysis. Analyses will be performed by Gas Chromatograph-Mass Spectrometer (30).

Clinical measures - Clinical rating and questionnaires will be administered. Treatment response will be operationally defined as 50% improvement from baseline in the HAM-D17 scores.

POTENTIAL RISKS/DISCOMFORTS

Diagnostic procedures and questionnaires: Some of the questions asked during the screening may be considered sensitive information, including drug use history and psychiatric history. Answering these questions may be psychologically discomforting to some subjects. There are also risks associated with loss of confidentiality.

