Once eligible for the study screening visit, they will be invited for study Day #1, which will begin with the presentation of the informed consent form. The consent form will detail the requirements of study participation (e.g., # of visits, type of data collected, time commitment, etc.) Subjects will be told that the purpose of the study is to evaluate neurophysiological measures to study the effect of ketamine on PND. Subjects will be informed that they will have to attend a total of 2 visits (screening/baseline and 1 study visit) and 2 follow up phone calls. Other information on the consent form will include a full description of study requirements, reimbursement, risks, benefits, alternatives, and the role of the local IRB. All questions will be answered before written consent is requested. Informed consent will be obtained only by the PI or a trained senior member of the staff (e.g. study coordinator).

The research protocol, consent form, and all assessment/advertising materials will be reviewed and approved by the Committee for the Protection of Human Subjects (CPHS) at UTH.

Protections against risk

- 1 **Risks related to diagnostic procedures/questionnaires:** As noted above, the primary risks related to these procedures are participant discomfort and loss of confidentiality. Regarding participant discomfort, we will make clear that we ask for this sensitive information as part of the consent process. Further, while subjects may be uncomfortable reporting these issues, the risks of serious sequelae are extremely low. Regarding confidentiality, we have rigorous procedures in place to ensure confidentiality of data.

including locked cabinets for confidential files, participant coding, secure computer systems, and rigorous training of personnel. Computer systems are secure and strictly monitored by University IT staff. Laboratory staffers are trained in confidentiality of participant information. No information is allowed to leave the lab or to be accessed by a computer outside of the university's secure computer system, and all data are further protected by permissions and passwords given only to necessary research personnel. No information will be published in a form in which the participant can be identified. We will also obtain a Certificate of Confidentiality for this study to provide additional protection for sensitive information.

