Potential benefits of the proposed research to the participants and others

All assessment and services provided in these studies will be free. The treatments may help in PND and prevent relapse. Subjects will be told if the unusual information is discovered during the study that will make a difference in treatment for this or other problems. By taking part in this research, subjects will help others with similar problems because this study is likely to identify how the treatment works and could also lead to the development of biomarkers for monitoring treatment response.

Importance of the knowledge to be gained

Research participation will help the patients in curing PND and possibly preventing relapse. The selected medication has shown preliminary evidence of benefit in helping patients with PND. PND is highly prevalent and leads to devastating consequences on a personal and societal level. Further, this study will pilot new approaches to evaluating treatments that may lead to more personalized and effective treatments for PND. The above-stated risks are relatively mild in degree and procedures have been designed to minimize their probability. We believe this protocol has an extremely favorable risk/benefit ratio. The psychiatry department has an excellent track record in conducting similar controlled trials with the utmost attention to safety.

Reimbursement

Patients will be provided \$20 for their participation in the screening visit if they qualify to complete the rest of the study. Patients will also be compensated \$100 if they complete the ketamine infusion study visit.

Transportation during infusion days

Patients will be asked to be accompanied by a caregiver that will be able to transport them after the ketamine infusion and to ensure that the patients arrive home safely. If patients are unable to provide a caregiver that can transport them, we will pay for transportation up to \$50 for infusion days and will call the patient to ensure safe arrival.

Follow up plan

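### The consent section tells patients of one study visit, two calls and a neurophysiological purpose, which contradicts the two-infusion crossover and its stated aims

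*Combined protocol and SAP*

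**What the plan says.** The paragraph on recruitment and informed consent, under Adequacy Of Protection Against Risks, sets out what participants are to hear. On purpose: "Subjects will be told that the purpose of the study is to evaluate neurophysiological measures to study the effect of ketamine on PND". On commitment, they are to be informed that "they will have to attend a total of 2 visits (screening/baseline and 1 study visit) and 2 follow up phone calls". The same paragraph also says that the form will detail items such as the number of visits and the time commitment, and will describe the study requirements in full. The ethics committee is to review and approve the protocol and the form.

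Elsewhere the protocol describes a different study:

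- **Objective** (Primary Hypotheses and Specific Aims): "The main objective of this study is to investigate the rapid antidepressant effect of low sub-anesthetic dose of ketamine in PND". The aim adds safety and pharmacokinetics, and the hypotheses add a comparison of 0.5 mg/kg with 0.2 mg/kg.
- **Infusions** (Research Design and Methods): "There will be two appointments where they will be administered a single intravenous infusion of Ketamine", with "a second infusion visit where they will receive the infusion that was not given on the first visit". The order is randomised and blinded, and the gap is at least 7 days.
- **Procedures** (Placement of IV): "For both of the infusion days, after the initial evaluation is done, patients will be placed one intravenous line in each arm".
- **Schedule of assessments**: separate columns for Infusion Day 1 and Infusion Day 2.
- **Calls**: Research Design and Methods has one call after the first infusion and two after the second. Medical Monitoring has calls on days 1, 2 and 7 after infusion.
- **Payment** (Reimbursement): $100 is due to patients "if they complete the ketamine infusion study visit", in the singular.

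**The concern.** The consent paragraph is not background. It tells staff what to say before a patient signs. The number of drug exposures, the time commitment and the purpose are central to that conversation, and the paragraph itself names the number of visits and the time commitment as items for the form.

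The omitted visit is a second ketamine exposure at a different, blinded dose. The protocol's own risk text reports that early hypertensive episodes and tachycardia predict haemodynamic changes at later infusions, so a second infusion is something a patient would want to weigh. Study length matters too, because the population includes women who would stop breastfeeding in order to take part.

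**Working it through.** No formula applies. The check is a count, section against section. The consent paragraph's own total is arithmetically sound: 1 screening/baseline visit + 1 study visit = 2 visits. It simply does not describe this design.

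| Item | Consent paragraph | Rest of protocol | Source |
|---|---|---|---|
| In-person visits | 2 | 1 screening + 2 infusion days = 3 | Research Design and Methods; schedule |
| Infusion visits | 1 | 2 | Research Design and Methods; Placement of IV; schedule |
| Follow-up calls | 2 | 1 + 2 = 3 | Research Design and Methods; schedule |
| Follow-up calls, other text | 2 | 3 × 1 = 3, or 3 × 2 = 6 | Medical Monitoring (days 1, 2 and 7, applied once or after each infusion) |
| Purpose | Neurophysiological measures | Antidepressant effect, safety, pharmacokinetics | Primary Hypotheses and Specific Aims |

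**Visits.** Patients would be told of 2 of 3 visits, and of 1 of 2 infusion visits (50%).

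**Calls.** No schedule elsewhere in the protocol gives 2 calls over the whole study. The two fuller accounts also differ from each other: Research Design and Methods has no day 2 call and no day 7 call after the first infusion, while Medical Monitoring does not say whether its three calls follow one infusion or both. The same-day call to confirm safe arrival home is not counted here.

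**Purpose.** The listed assessments are a diagnostic interview, clinical rating scales, physical examination, vital signs, urine tests and blood samples for ketamine and norketamine. None is neurophysiological. The EKG and pulse oximetry during infusion are for safety monitoring.

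**Likely origin (an inference).** One screening visit, one study visit and two calls would fit a single-infusion study followed up on days 1 and 7. Other text points the same way: General Information speaks of a single administration, and the alternate plans in the Data Analysis Plan treat giving two doses instead of one as a later change needing an amendment. The consent paragraph may be carried over from such a design, but the documents do not say so.

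**The case against.** The strongest reply is that the consent form itself is not in the documents, and that its absence is no fault of the plan. The same paragraph promises that the form will set out the visits, the time commitment and the requirements in full, under ethics committee review. A correct form may well exist. This stands as a limit on the consequence. A reader might infer that patients will consent to half of the actual exposure; the documents do not show that. Half is also exact only for infusion visits. By cumulative dose (0.5 + 0.2 = 0.7 mg/kg), one visit is 0.5/0.7 = 71% or 0.2/0.7 = 29%, depending on order. The promise does not remove the contradiction, however, because a full and accurate form would disagree with the explicit counts in the same paragraph.

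On purpose, it can be said that the protocol mentions biomarkers and markers of treatment response. It does, but it names no neurophysiological one and schedules none.

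Three further inferences are tempting and should not be drawn:

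- **Loss of power.** A reader might argue that patients surprised by a second infusion will leave after the first, costing pairs. Nothing in the documents links the wording to dropout. The Data Analysis Plan's effect size of 1.2 and its paired t-test concern change from baseline, and a patient who leaves after the first infusion and its day 1 call still supplies that pair. No effect size is given for the contrast between doses, so no power loss can be calculated for it.
- **Lines and blood samples.** The consent paragraph gives no number for either, so there is no stated figure to set against the actual one.
- **Payment.** The singular wording may mean a payment for each visit, and the next paragraph, on transportation, speaks of infusion days in the plural. It is ambiguous and does not prove a single-infusion study.

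**Conclusion.** The point holds as an internal contradiction. The consent paragraph is wrong as written on three counts: visits (2 against 3, with 1 infusion visit against 2), calls (2 against 3, or up to 6) and purpose. It goes beyond a clerical slip, because staff who followed it would misdescribe a second ketamine exposure. It should be corrected.

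Harm to patients is conditional: it arises if the form or the consent discussion follows the paragraph rather than the schedule. The count takes the crossover as the intended design, which the hypotheses, methods, line placement and schedule all support. The conclusion does not rest on any effect on retention, power or sample size.

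**What to change.** Amend the wording as follows:

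1. In the recruitment and informed consent paragraph, replace the purpose with the one in the aims. Describe the commitment as screening plus two infusion visits at least 7 days apart, at two blinded doses in randomised order, as the methods section has it.
2. Reconcile the calls in Research Design and Methods and the schedule with those in Medical Monitoring, and carry the agreed number into the consent paragraph.
3. In Reimbursement, say whether the $100 applies to each infusion visit or to both together.
4. Check the consent form line by line against the schedule, and correct it if it repeats the present counts or purpose.

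The cost is a protocol wording amendment and, if the form is affected, a revised form, both through ethics review. Sample size, design and analysis are unchanged.

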breastfeeding mother and the baby. Ketamine and its metabolites will be evaluated in PND patients receiving ketamine 0.5 mg/kg or 0.2 mg/kg at 30 mins, 2 hours and 4-5 hrs after ketamine infusion. All adverse medical and psychiatric events with onset or worsening after the administration of ketamine will be included in the analysis.

The proposed experiment will be a proof-of-concept study in which we will evaluate the safety, pharmacokinetics, and efficacy of ketamine 0.5 mg/kg and 0.2 mg/kg over 40 minutes in a double-blinded and crossover fashion separated over one week (5) (dose used in antidepressant clinical trials) in PND patients who are not currently breastfeeding. The primary outcome measure of efficacy will be the Hamilton Depression Rating Scale (HAM-D-17) at 24 hours and additional secondary anxiety and mood scales. (6). Any adverse medical and psychiatric events will be recorded and summarized. Ketamine and its metabolites will be evaluated at 30 mins, 2 hours and 24 hrs.

Hypothesis 1): Ketamine will significantly decrease (>50%) in HAM-D17 scores at 24 hrs after infusion from baseline. The 0.5 mg/kg dose will be more efficacious than 0.2 mg/kg in improving depression symptoms.

Hypothesis 2) Ketamine will improve anxiety symptoms in PND (as measured using HAM-Anxiety and EPDS) at 24 hrs after infusion in patients with PND. Anxious subtypes are the most common subtype during a late postpartum period representing about 70 % of PND. (40)

Hypothesis 3) Ketamine infusion will be tolerated well by the patients with fewer side effects at 0.2 mg/kg compared to 0.5 mg/kg.

METHODS

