- 2 **Risks related to study medication:** The following procedures will be taken to safeguard against adverse medication events: (1) careful initial intake evaluation to determine eligibility based on inclusion/exclusion criteria; (2) thorough physical evaluation prior to infusion, consisting of physical examination, standard laboratory tests, electrocardiogram, urine toxicology screen, pregnancy test and vital signs; (3) Monitoring of concomitant illicit drug use at each visit with self-report, urine and/or breath testing; (4) Review of medication response, adverse events, and medication compliance with the study nurse; (5) Regular evaluation of all medical information. In the event that contraindicated medical conditions and/or other serious adverse symptoms arise after initiation of the medication, medication will be discontinued and the subject will be examined.
- 3 **Risks related to alternative treatments:** As noted above, we believe that our therapeutic interventions provide treatment that is considerably superior to most, if not all, treatment opportunities in the community. Nevertheless, we will refer patients to other facilities upon request or when required by other circumstances. We will also conduct regular literature searches on alternative treatments, and in the event that an alternative treatment emerges with clearly superior efficacy, we would suspend the current study and provide all participants with referrals for this alternative treatment.
- 4 **Study withdrawal:** The research study and participation is completely voluntary. Participants can withdraw from the study at any time without giving a reason and without any consequence. A decision not to take part or to stop being a part of the research project will not change the services available to them from the UTHSC-H, Department of Psychiatry or HCPC or CRU. The investigators could stop participation if an unfavorable or unexpected reaction is noticed.
- 5 **Unanticipated Hospitalizations:** If a patient needs to be hospitalized for worsening of symptoms or for their own personal safety, they will be removed from their study participation and their study treatment will end at that time.
- 6 **Risks of blood draw:** There are minimal risks involved in having the blood draw for the study. The blood sample will be drawn from a peripheral vein by a trained staff person. The risks involved are related to local bruising but these will be minimized by the use of trained personnel.

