Patients considered as participants of the study will be referred to [name] as a treating psychiatrist if they are not his patients. Patients who are referred by existing providers will return under the care of their care. If they have successful treatment with ketamine, they will be referred to a list of providers in the area of Houston that provide ketamine infusions as treatment for depressive symptoms, if the patient would want to consider continuing with the treatment as needed.

Data and Safety Monitoring Plan

The principal investigator will be responsible for the Data and Safety monitoring of the study.

Data monitoring plan

Data will be collected and stored as described above in Sources of Material and analyzed with primary outcomes as described in the Statistical Plan. Trained research assistants will enter data into an existing, relational database. Allowable input values will be restricted to standardized Access entry forms so as to maintain data integrity. All observations will be double-entered to verify the accuracy, with any problems detected discussed with the PI. If necessary, the re-training of research assistants will be conducted. Due to the comparatively small and initial nature of the current trial, interim data analysis is not planned.

Safety monitoring plan

During the screening, study applicants will undergo a complete psychological and physical exam to determine their eligibility and safety of their participation in this study, per inclusion/exclusion criteria detailed above. During the treatment phase of the study, participants will be asked about adverse events at each clinic visit and vital signs will be continuously monitored during the infusion and two hours after the infusion.

All adverse events (AEs) occurring during the course of the study will be collected, documented, and reported to the Principal Investigator. The occurrence of AEs will be assessed at baseline and each visit during the treatment phase of the study. The PI, in consultation with the co-investigators, will review any AE's as soon as they are reported. The study investigators will follow all AEs to the point of a satisfactory resolution. A study participant may have their medication discontinued or may be withdrawn from the study if the Study Physician determines it is the best decision in order to protect the safety of a participant. All AEs will be assessed to determine if they meet criteria for an SAE.

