Serious adverse events (SAEs), as defined by the FDA, will be evaluated at each visit. Any SAE, whether or not related to study medication, will be reported to the IRB within 24 hours. The initial SAE report will be followed by submission of a completed SAE report within 2 days. In the event that a patient either withdraws from the study or the investigator decides to discontinue a patient due to SAE, the patient will have appropriate follow-up medical monitoring. Monitoring will continue until the problem requiring hospitalization has resolved or stabilized with no further change expected, is clearly unrelated to study medication, or results in death. The outcome of SAEs will be periodically reported to IRB.

Inclusion of Women

The subjects will include only females, ages 18-45 years old, from various race/ethnic backgrounds, as reflected in the local community in the greater Houston area.

Inclusion of Minorities

Our study will include minority groups in proportions that will be representative of the ethnic/racial composition of the local community in Houston, Texas. Our projected numbers for minority enrollment are detailed in the enrollment table attached.

Inclusion of Children

Children will not be included in the study. The inclusion of children at this early stage would increase substantially the number of subjects needed for the overall project and would not be conducive to the perinatal nature of the study. At this time, we will focus on an adult population (ages 18-45 years old).

Prisoners and pregnant women

We are aware of the special protections afforded to prisoners per federal regulations. We will not actively recruit people who are incarcerated to participate in this study. We do, however, acknowledge the possibility of research participants in our target population being incarcerated during the study. If an active participant is incarcerated for an extended period of time, disenrollment from the study will be necessary. No research interaction or intervention will take place until an incarcerated participant is released from jail. Finally, neither the pregnant woman nor neonates will be enrolled in this study. Women will only be recruited postpartum and after having weaned their child.

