DATA ANALYSIS PLAN - General Data Analysis: The data analytic strategy will use generalized linear modeling. Statistical analyses will use SAS v.9.3. Preliminary data analyses will inspect baseline, treatment from baseline differences as well as correlations between baseline variables and specified outcomes. Baseline characteristics will be compared within groups using Student's t-tests for continuous data and chi-square tests for categorical data.

Sample size justification: our power calculation is guided by a previous study - intravenous ketamine in TRD patients (28) with effect size (Cohen's $d = 1.46$) or Brexanolone in PND (effect size 1.2) (12, 32). For an effect size 1.2, a total of 10 PND patients will be required for within-subject design with probability 95 % that the study will detect a treatment difference at a one-sided 0.05 significance level.

Hypothesis: Based on previous studies (33, 34) and our pilot Ketamine TRD patient data, we predict that ketamine infusion compared to baseline will significantly decrease HAM-D scores in PND patient at 24 hrs. The severe anxious subtype will have prominent improvement.

Analysis: We will use linear regression to assess associations between improvements in depressive symptoms (change in the HAM-D from baseline using LOCF). A paired t-test was performed to evaluate the key efficacy measure - change from baseline in HAMD total score. We will also perform a secondary analysis comparing change from baseline to endpoint using last observation carried forward (LOCF) using a paired sample t-test. Secondary outcomes are safety and tolerability measures, including treatment-emergent AEs and changes from EPDS, GAD-7, PHQ-9, and C-SSRS. We will also investigate specific markers for treatment response.

Alternate plans: The proposal applies the widely used ketamine sub-anesthetic dose (0.5 mg/kg) as a treatment for PND. If the effect is less clear or patient experiences any adverse effects, alternate strategies will be explored (two doses of ketamine instead of single or low dose 0.3 mg/kg if adverse effects etc. respectively). Patient safety and tolerability will be the most important guiding principle. This will require an amendment in the protocol and an updated consent.

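### Hospitalisation for worsening ends study participation as well as infusions, so a 24-hour HAM-D-17 score not yet taken goes missing for an outcome-related reason

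*Combined protocol and SAP*

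**What the plan says.** Four parts of the protocol bear on this point.

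- **Removal rule.** Protections against risk, item 5 (Unanticipated Hospitalizations), has the trigger "If a patient needs to be hospitalized for worsening of symptoms or for their own personal safety" and the consequence "they will be removed from their study participation and their study treatment will end at that time". Ending treatment and ending participation are coupled.
- **Follow-up after discontinuation.** For a patient who leaves because of a serious adverse event, the safety monitoring text says "the patient will have appropriate follow-up medical monitoring". It mentions no efficacy rating, and no other section schedules ratings after removal.
- **Endpoint and design.** The Aims state: "The primary outcome measure of efficacy will be the Hamilton Depression Rating Scale (HAM-D-17) at 24 hours". Research Design and Methods gives the two doses "in a double-blinded and crossover fashion separated by minimum 7 days, with the order being randomized and balanced across subjects". The assessment schedule also has HAM-D-17 rated before and after each infusion on the infusion day and at the follow-up calls.
- **Analysis.** The Analysis paragraph of the Data Analysis Plan says "A paired t-test was performed to evaluate the key efficacy measure - change from baseline in HAMD total score", with no missing-data rule for that test. The regression uses "change in the HAM-D from baseline using LOCF", and a secondary paired t-test also uses LOCF. No analysis set is defined, and nothing says how a removed patient counts towards response, defined as a 50% improvement in HAM-D-17.

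**The concern.** Worsening depression is what the trial measures, so a rating lost because of hospitalisation for worsening is informatively missing. A patient hospitalised before the 24-hour call has no primary score for that infusion. Left out of the paired t-test, she takes a failure with her. Under LOCF she receives a score from before the infusion or from a few hours after it. The protocol's background reports improvement already visible at about two hours, so the same-day score may be a favourable one. If she has since deteriorated, either route makes the change from baseline look better than it was. With 10 patients and no allowance for losses, one such case is a tenth of the data.

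**Working it through.** **1. The plan's own sample size.** Inputs from the Sample size justification: effect size 1.2, one-sided 0.05, 95% power, within-subject design. For a paired t-test, power = P(T > t(0.95, n−1)), with T noncentral t on n−1 degrees of freedom and noncentrality 1.2√n. This gives 0.9675 at n = 10 and 0.9484 at n = 9, so 10 is the smallest n reaching 95% and the stated figure reproduces. At the same effect size, losing one, two or three patients leaves power of 0.948, 0.919 or 0.874. Loss of power is therefore minor; bias is the issue.

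**2. What is lost, by timing of hospitalisation.**

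- *Before a 24-hour rating:* the primary score for that infusion is missing.
- *After the 24-hour rating of infusion 1, before infusion 2:* the first-dose score stands. There is no second-dose score, because treatment ends.
- *After the 24-hour rating of infusion 2:* both primary scores stand. Only the day 7 ratings are affected.

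**3. Effect on the mean change, one patient of the first kind in 10.** The scores are assumptions, not trial figures. The other nine each change by −10 HAM-D points (a 50% fall from a baseline of 20), and she truly changes by +5. The 5 points are borrowed from the Stopping Rules only to set a scale; that rule uses 21 items and weekly visits.

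| Handling | Mean change | Improvement overstated by |
|---|---|---|
| Rated at 24 h | (9 × (−10) + 5)/10 = −8.5 | none |
| Omitted | (9 × (−10))/9 = −10.0 | 1.5 |
| Carried forward at change 0 | (−90 + 0)/10 = −9.0 | 0.5 |
| Carried forward at change −5 | (−90 − 5)/10 = −9.5 | 1.0 |
| Carried forward at change −10 | (−90 − 10)/10 = −10.0 | 1.5 |

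In general, LOCF overstates improvement by (true change − carried change)/10 per patient. If her same-day score already showed the full worsening (+5), the overstatement would be zero.

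With two such patients, the mean is (8 × (−10) + 2 × 5)/10 = −7.0 if rated, −10.0 if both are omitted, and −8.0 to −10.0 under LOCF. The overstatement is 1.0 to 3.0 points.

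**4. Effect on the response rate.** Separately, assume 7 responders among 10, with the hospitalised patient a non-responder. Counted as such: 7/10 = 70%. Omitted: 7/9 = 77.8%. Carried forward at an early response: 8/10 = 80%.

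**The case against.** The strongest reply is that this may never happen. Biasing a 24-hour score takes a hospitalisation for worsening within about a day of dosing. Patients at serious and imminent suicidal risk are excluded at entry, each patient is assessed before and after infusion and observed for hours, and the documents give no hospitalisation rate. A patient who deteriorates that fast may also have a poor same-day score, in which case LOCF would carry non-response. All of this stands and limits the point to a contingency.

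Several stronger readings are tempting, and the documents do not support them.

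- *A reader might infer that treatment failures in general drop out of the efficacy result.* They do not. Any 24-hour score taken before hospitalisation remains.
- *A reader might infer that the coupling damages the two-dose comparison and that keeping the patient in the study would repair it.* Between infusions, the second-dose score is lost because treatment ends, and no follow-up rating can replace it. On the Research Design and Methods account of the calls, none remains after day 1 following infusion 1.
- *A reader might count C-SSRS among the ratings to be recovered.* The schedule lists it at screening and after each infusion, not at the calls.
- *A reader might extend the fault to the Safety monitoring plan.* That text already separates the two steps: "A study participant may have their medication discontinued or may be withdrawn from the study if the Study Physician" judges this best for her safety. The coupling is in item 5 alone.
- *A reader might take it as stated that the paired t-test omits her.* That is the likely default, but the plan is silent. The lack of ratings after removal is likewise inferred from the end of participation and the absence of any provision.

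It is also fair to say that inpatient ratings may reflect new treatment. Whether to use them is a choice to make in advance.

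**Conclusion.** The point holds in a limited form. As written, item 5 together with the Analysis paragraph can make a 24-hour HAM-D-17 score missing because the patient worsened. The likely handling, omission or LOCF, would then favour ketamine unless the carried score already reflects the worsening. Under the assumed scores, one such patient in 10 overstates mean improvement by roughly 0.5 to 1.5 HAM-D points, and omitting her moves response from 70% to 78%. These figures show scale only; they are not a forecast. Later hospitalisation touches only day 7, and hospitalisation between infusions costs a second-dose score that no follow-up rule can restore. This is an inexpensive improvement worth making before data are seen, not a flaw that undermines the trial.

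**What to change.** **Protections against risk, item 5.** State that study infusions end but that, unless the patient withdraws consent, the telephone ratings already scheduled for the last infusion received are still sought: HAM-D-17, MADRS, EPDS, GAD-7 and BDI. Research Design and Methods describes a call one day after infusion 1 and calls one and seven days after infusion 2, whereas Medical Monitoring lists days 1, 2 and 7. These must be reconciled so that it is clear which ratings are meant.

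**Data Analysis Plan, Analysis paragraph.** Add that:

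- hospitalisation for worsening before a 24-hour rating counts as non-response to that infusion in the responder analysis;
- an earlier post-infusion score is not carried forward for such a patient;
- an observed 24-hour score, if obtained, is used in the HAM-D change analysis; otherwise a sensitivity analysis assigns her no improvement, or a worsening;
- all such cases, including those between infusions, are reported by dose and sequence.

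The clinical decision to end infusions is unchanged.

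**Cost.** Protocol wording and a few analysis sentences. No visits are added, because the calls are already planned. Some patients will be unreachable, inpatient ratings may reflect new treatment, and the reported response may be slightly lower.
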